10.84 DEFINITIONS

SERIOUS ADVERSE EVENTS

A *Serious Adverse Event (SAE)* is any untoward medical occurrence that at any dose:

- results in death
- is life-threatening (defined as an event in which the subject was at risk of death at the time of the event; it does not refer to an event which hypothetically might have caused death if it were more severe)
- requires inpatient hospitalization or causes prolongation of existing hospitalization (see **NOTE** below)
- results in persistent or significant disability/incapacity
- is a congenital anomaly/birth defect
- is an important medical event (defined as a medical event(s) that may not be immediately life-threatening or result in death or hospitalization but, based upon appropriate medical and scientific judgment, may jeopardize the subject or may require intervention [eg, medical, surgical] to prevent one of the other serious outcomes listed in the definition above.) Examples of such events include, but are not limited to, intensive treatment in an emergency room or at home for allergic bronchospasm; blood dyscrasias or convulsions that do not result in hospitalization.)
- Potential drug induced liver injury (DILI) is also considered an important medical event.
- Suspected transmission of an infectious agent (eg, pathogenic or nonpathogenic) via the study drug is an SAE.
- Although pregnancy, overdose, and cancer are not always serious by regulatory definition, these events must be handled as SAEs.

NOTE: (PI- determines if this information should be included. This is provided as supplemental information that is included in BMS-

sponsored trials)

The following hospitalizations are not considered SAEs in BMS clinical studies:

- a visit to the emergency room or other hospital department < 24 hours, that does not result in admission (unless considered an important medical or life-threatening event)
- elective surgery, planned prior to signing consent
- admissions as per protocol for a planned medical/surgical procedure
- routine health assessment requiring admission for baseline/trending of health status (eg, routine colonoscopy)
- Medical/surgical admission other than to remedy ill health and planned prior to entry into the study. Appropriate documentation is required in these cases
- Admission encountered for another life circumstance that carries no bearing on health status and requires no medical/surgical intervention (eg, lack of housing, economic inadequacy, caregiver respite, family circumstances, administrative reason).

ADVERSE EVENTS

An Adverse Event (AE) is defined as any new untoward medical occurrence or worsening of a preexisting medical condition in a clinical investigation subject administered an investigational (medicinal) product and that does not necessarily have a causal relationship with this treatment. An AE can therefore be any unfavorable and unintended sign (such as an abnormal laboratory finding), symptom, or disease temporally associated with the use of investigational product, whether or not considered related to the investigational product.

The causal relationship to study drug is determined by a physician and should be used to assess all adverse events (AE). The causal relationship can be one of the following:

Related: There is a reasonable causal relationship between study drug administration and the AE.

Not related: There is not a reasonable causal relationship between study drug administration and the AE.

The term "reasonable causal relationship" means there is evidence to suggest a causal relationship.

Adverse events can be spontaneously reported or elicited during open-ended questioning, examination, or evaluation of a subject. (In order to prevent reporting bias, subjects should not be questioned regarding the specific occurrence of one or more AEs.)

NONSERIOUS ADVERSE EVENT

- Nonserious Adverse Events are to be provided to BMS in aggregate via interim or final study reports as specified in the agreement or, if a regulatory requirement [e.g. IND US trial] as part of an annual reporting requirement.
- Nonserious AE information should also be collected from the start of a placebo lead-in period or other observational period intended to establish a

baseline status for the subjects.

A **nonserious adverse event** is an AE not classified as serious.

Nonserious Adverse Event Collection and Reporting

The collection of nonserious AE information should begin at initiation of study drug. All nonserious adverse events (not only those deemed to be treatment-related) should be collected continuously during the treatment period and for a minimum of 100 days following the last dose of study treatment.

Nonserious AEs should be followed to resolution or stabilization, or reported as SAEs if they become serious. Follow-up is also required for nonserious AEs that cause interruption or discontinuation of study drug and for those present at the end of study treatment as appropriate.

Laboratory Test Abnormalities

All laboratory test results captured as part of the study should be recorded following institutional procedures. Test results that constitute SAEs should be documented and reported as such.

The following laboratory abnormalities should be documented and reported appropriately:

- any laboratory test result that is clinically significant or meets the definition of an SAE
- any laboratory abnormality that required the subject to have study drug discontinued or interrupted
- any laboratory abnormality that required the subject to receive specific corrective therapy.

10.85 Potential Drug Induced Liver Injury (DILI)

Wherever possible, timely confirmation of initial liver-related laboratory abnormalities should occur prior to the reporting of a potential DILI event. All occurrences of potential DILIs, meeting the defined criteria, must be reported as SAEs. Potential drug induced liver injury is defined as:

- 1) ALT or AST elevation > 3 times upper limit of normal (ULN)

AND

- 2) Total bilirubin > 2 times ULN, without initial findings of cholestasis (elevated serum alkaline phosphatase)

AND

- 3) No other immediately apparent possible causes of AST/ALT elevation and hyperbilirubinemia, including, but not limited to, viral hepatitis, pre-existing chronic or acute liver disease, or the administration of other drug(s) known to be hepatotoxic.

10.86 Pregnancy

If, following initiation of the investigational product, it is subsequently discovered that a study subject is pregnant or may have been pregnant at the time of investigational product exposure, including during at least 6 half lives after product administration, the investigational product will be permanently

discontinued in an appropriate manner (eg, dose tapering if necessary for subject safety).

The investigator must immediately notify Worldwide Safety @BMS of this event via the Pregnancy Surveillance Form in accordance with SAE reporting procedures.

Follow-up information regarding the course of the pregnancy, including perinatal and neonatal outcome and, where applicable, offspring information must be reported on the Pregnancy Surveillance Form [provided upon request from BMS]

Any pregnancy that occurs in a female partner of a male study participant should be reported to BMS. Information on this pregnancy will be collected on the Pregnancy Surveillance Form.

10.87 Overdose

An overdose is defined as the accidental or intentional administration of any dose of a product that is considered both excessive and medically important. All occurrences of overdose must be reported as an SAE.

10.88 Other Safety Considerations

Any significant worsening noted during interim or final physical examinations, electrocardiograms, x-rays, and any other potential safety assessments, whether or not these procedures are required by the protocol, should also be recorded as a nonserious or serious AE, as appropriate, and reported accordingly.

11.0 Treatment Evaluation

Lugano Classification Response Criteria

11.1 Response Considerations

Schedule of Evaluations: PET/CT scans are required at baseline for all patients. In addition to a baseline PET/CT scan, confirmatory scans should also be obtained post Cycle 4, 8, and 12 of chemotherapy, then a CT scan every 16 weeks thereafter. During observation, CT scan should be obtained every 3 months during the first year to evaluate for disease progression.

Definitions for clinical response for patients with lymphoma are from the recently revised Cheson's et al criteria published in 2014, derived from the original criteria published in 2007. (Cheson et al, 2014)(Cheson et al, 2007). Lymph node measurements should be taken from the CT portion of the PET/CT, or other dedicated CT scans where applicable. Measurement of lymphadenopathy for purposes of assessing for PR will be determined by adding the sum of the products of the maximal perpendicular diameters of measured lesions (SPD). The PPD of a single node is sufficient to evaluate for PD (see Table 11.2). Measurable extranodal disease should be assessed in a manner similar to that for nodal disease. For these recommendations, the spleen is considered nodal disease. Disease that is only assessable (eg, pleural effusions, bone lesions) will be recorded as present or absent only, unless, while an abnormality is still noted by imaging studies or physical examination, it is found to be histologically and pathologically negative.

Response is based on PET/CT based on the revised 2014 Lugano Classification. (Cheson et al, 2014).

Progressive disease is based on either PET-CT based (PMD) or CT based (PD) response criteria. PET confirmation of progressive disease is per physician discretion.

11.2 Pseudoprogression

Some therapeutic agents, particularly immunotherapeutics, display different patterns of anti-tumor response, which may include a period of increasing tumor burden followed by a response, stable disease followed by slow decline in tumor burden, or even a response in the presence of new lesions (Chow, 2013; Wolchok et al., 2009). Immune-mediated responses may take longer to manifest than those from cytotoxic agents. In other cancer settings, a phenomenon called "tumor flare" or pseudoprogression has also been described, in which increased metabolic activity in FDG-PET is observed on posttreatment PET-CT which represents a biologic effect on the tumor and its microenvironment. (REF)

In order to avoid falsely assigning disease progression during the the study, a subject whose radiologic disease assessment is indicative of progression may, at the discretion of the Investigator, continue on treatment pending a repeat scan, if all of the following criteria are met:

- absence of symptomatic or clinical progression
- stable performance status
- adequate tolerance to nivolumab
- treating beyond progression does not delay an intervention felt to be in the patient's best interest

If the second confirmatory scan indicates unequivocal disease progression, the

subject will be discontinued from treatment. The date of the first scan indicating progression will be used for analysis purposes. If however the second scan indicates a reduction in tumor burden or stable disease from the baseline scan, the subject may continue on treatment in the absence of unacceptable toxicity or other reason for treatment discontinuation.

Notwithstanding, the Investigator is free to remove the patient from treatment at any time during the study if it is felt to be in the patient's best interest.

11.3 Lugano Classification Response criteria (Cheson et al, 2014)

	PET-CT Based Response	CT-Based Response
Complete Response	Complete metabolic response (CMR)	Complete radiologic response (CR) (all of the following)
Lymph nodes and extralymphatic sites	Score 1, 2, or 3* with or without a residual mass on 5PS† It is recognized that in Waldeyer's ring or extranodal sites with high physiologic uptake or with activation within spleen or marrow (eg, with chemotherapy or myeloid colony-stimulating factors), uptake may be greater than normal mediastinum and/or liver. In this circumstance, complete metabolic response may be inferred if uptake at sites of initial involvement is no greater than surrounding normal tissue even if the tissue has high physiologic uptake	Target nodes/nodal masses must regress to ≤1.5 cm in LDi No extralymphatic sites of disease
Nonmeasured lesion	Not applicable	Absent
Organ enlargement	Not applicable	Regress to normal
New lesions	None	None
Bone marrow	No evidence of FDG-avid disease in marrow	Normal by morphology; if indeterminate, IHC negative
Partial Response	Partial metabolic response (PMR)	Partial remission (PR) (all of the following)
Lymph nodes and extralymphatic sites	Score 4 or 5† with reduced uptake compared with baseline and residual mass(es) of any size At interim, these findings suggest responding disease At end of treatment, these findings indicate residual disease	≥50% decrease in SPD of up to 6 target measurable nodes and extranodal sites When a lesion is too small to measure on CT, assign 5 mm X 5 mm as the default value When no longer visible, 0 X 0 mm For a node >5 mm X 5 mm, but smaller than normal, use actual measurement for calculation
Nonmeasured lesions	Not applicable	Absent/normal, regressed, but no increase
Organ enlargement	Not applicable	Spleen must have regressed by >50% in length beyond normal
New lesions	None	None

	PET-CT Based Response	CT-Based Response
Bone marrow	Residual uptake higher than uptake in normal marrow but reduced compared with baseline (diffuse uptake compatible with reactive changes from chemotherapy allowed). If there are persistent focal changes in the marrow in the context of a nodal response, consideration should be given to further evaluation with MRI or biopsy or an interval scan	Not Applicable
No Response or Stable Disease	No metabolic response (NMR)	Stable disease (SD)
Target nodes/nodal masses, extranodal lesions	Score 4 or 5 with no significant change in FDG uptake from baseline at interim or end of treatment	<50% decrease from baseline in SPD of up to 6 dominant, measurable nodes and extranodal sites; no criteria for progressive disease are met
Nonmeasured lesions	Not applicable	No increase consistent with progression
Organ enlargement	Not applicable	No increase consistent with progression
New lesions	None	None
Bone marrow	No change from baseline	Not Applicable
Progressive disease	Progressive metabolic disease (PMD)	Progressive disease (PD) requires at least 1 of the following
Individual target nodes/nodal masses	Score 4 or 5 with an increase in intensity of uptake from baseline and/or	PPD progression: An individual node/lesion must be abnormal with: LDi >1.5 cm and Increase by ≥50% from PPD nadir and An increase in LDi or SDi from nadir 0.5 cm for lesions ≤2 cm 1.0 cm for lesions >2 cm In the setting of splenomegaly, the splenic length must increase by >50% of the extent of its prior increase beyond baseline (eg, a 15 cm spleen must increase to >16 cm). If no prior splenomegaly, must increase by at least 2 cm from baseline New or recurrent splenomegaly
Extranodal lesions	New FDG-avid foci consistent with lymphoma at interim or end-of-treatment assessment	
Nonmeasured lesions	None	New or clear progression of preexisting nonmeasured lesions
New lesions	New FDG-avid foci consistent with lymphoma rather than another etiology (eg, infection, inflammation). If uncertain regarding etiology of new lesions, biopsy or interval scan may be considered	Regrowth of previously resolved lesions A new node >1.5 cm in any axis A new extranodal site >1.0 cm in any axis; if <1.0 cm in any axis, its presence must be unequivocal and must be attributable to lymphoma

	PET-CT Based Response	CT-Based Response
		Assessable disease of any size unequivocally attributable to lymphoma
Bone marrow	New or recurrent FDG-avid foci	New or recurrent involvement

Abbreviations: 5PS, 5-point scale; CT, computed tomography; FDG, fluorodeoxyglucose; IHC, immunohistochemistry; LDi, longest transverse diameter of a lesion; MRI, magnetic resonance imaging; PET, positron emission tomography; PPD, cross product of the LDi and perpendicular diameter; SDi, shortest axis perpendicular to the LDi; SPD, sum of the product of the perpendicular diameters for multiple lesions.
 
*A score of 3 in many patients indicates a good prognosis with standard treatment, especially if at the time of an interim scan. However, in trials involving PET where de-escalation is investigated, it may be preferable to consider a score of 3 as inadequate response (to avoid undertreatment). Measured dominant lesions: Up to six of the largest dominant nodes, nodal masses, and extranodal lesions selected to be clearly measurable in two diameters. Nodes should preferably be from disparate regions of the body and should include, where applicable, mediastinal and retroperitoneal areas. Non-nodal lesions include those in solid organs (eg, liver, spleen, kidneys, lungs), GI involvement, cutaneous lesions, or those noted on palpation. Nonmeasured lesions: Any disease not selected as measured, dominant disease and truly assessable disease should be considered not measured. These sites include any nodes, nodal masses, and extranodal sites not selected as dominant or measurable or that do not meet the requirements for measurability but are still considered abnormal, as well as truly assessable disease, which is any site of suspected disease that would be difficult to follow quantitatively with measurement, including pleural effusions, ascites, bone lesions, leptomeningeal disease, abdominal masses, and other lesions that cannot be confirmed and followed by imaging. In Waldeyer's ring or in extranodal sites (eg, GI tract, liver, bone marrow), FDG uptake may be greater than in the mediastinum with complete metabolic response, but should be no higher than surrounding normal physiologic uptake (eg, with marrow activation as a result of chemotherapy or myeloid growth factors).
 
†PET Deauville 5PS: 1, no uptake above background; 2, uptake \leqmediastinum; 3, uptake $>$mediastinum but \leqliver; 4, uptake moderately $>$liver; 5, uptake markedly higher than liver and/or new lesions; X, new areas of uptake unlikely to be related to lymphoma.
		

12.0 Descriptive Factors

- 12.1 Histologic subtype: Peripherheral T-Cell Lymphoma NOS vs. Other
- 12.2 Prior ASCT vs No ASCT

13.0 Treatment/Follow-up Decision at Evaluation of Patient

- 13.1 Criteria for continuation of treatment
 - Patients who are CR/CMR, PR/PMR, or SD will continue treatment per protocol.
- 13.2 Progressive Disease (PD)
 - Patients who develop PD while receiving therapy will go to the event-monitoring phase.
- 13.3 Off protocol for reasons other than PD
 - Patients who go off protocol treatment for reasons other than PD will go to the event-monitoring phase per Section 18.0.
- 13.4 Observation
 - If the patient has achieved CR/CMR, PR/PMR, or SD, the patient will be observed for

four visits: 1) 35±7 days after last treatment; 2) 100-120 days post treatment; 3) 230-250 days post treatment; and 4) 330-390 days post treatment, during observation (Active Monitoring Phase) until the patient goes to event monitoring for up to 5 years from time of registration (see [Section 4.2](#)).

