20.0 References.....	62
Appendix I ECOG Performance Status.....	63
Appendix II Adverse Event Management Algorithms.....	64
Appendix III Specimen Checklist and Shipping Instructions.....	71

Schema

Progressive Disease³ at any time Unacceptable adverse Events Patient refusal	→	Event Monitoring per Section 4.2
--	---	---

¹ Cycle length initial treatment (first 8 cycles): 14 days

Cycle length continuation treatment (beginning with Cycle 9): 28 days

²PET-CT based response criteria: Stable Disease (SD), CR – complete response, PR – partial response (See [Section 11.0](#))

³PET-CT based response criteria. Progressive disease (PD) (See [Section 11.0](#)). PET confirmation of PD is per physician discretion.

Generic name: Nivolumab Brand name(s): Opdivo® Mayo Abbreviation: BMS936558 Availability: Mayo Cancer Center Pharmacy
--

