7.2 Return to consenting institution

For this protocol, the patient must return to the consenting institution for evaluation at least every 14 days during initial treatment and every 28 days during continuation therapy.

After therapy discontinuation, the patient must return to the institution for four visits: 1) 35±7 days after last treatment; 2) 100-120 days post treatment; 3) 230-250 days post treatment; and 4) 330-390 days post treatment, during observation (Active Monitoring Phase) until the patient goes to event monitoring per Section 13.0.

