8.2 Dose Delay Criteria for Nivolumab

See Management Algorithms ([Appendix II](#))

→ → Use the NCI Common Terminology Criteria for Adverse Events (CTCAE) version 4.0* unless otherwise specified ← ←

CTCAE System/Organ/Class (SOC)	Event	Agent	Action
Investigations	Alanine aminotransferase increased, Aspartate aminotransferase increased, and/or Blood bilirubin increased	Nivolumab	
If a patient has a baseline AST/ALT that is within the normal limits, delay dosing for nivolumab-related \geqGrade 2 (>3-5 x ULN) elevations and start corticosteroids at 0.5 to 1 mg/kg/day prednisone equivalents. Nivolumab may be resumed if the value improves to Grade 1 (≤ 3 x ULN) or better.
 
If a patient has a baseline AST/ALT in the Grade 1 range (ULN to ≤ 3 x ULN), delay dosing for nivolumab-related \geqGrade 3 (>5 to 8 x ULN) elevations and start corticosteroids at 1 to 2 mg/kg/day prednisone equivalents. Nivolumab may be resumed if the value improves to Grade 2 (>3 to 5 x ULN) or better.
 
If a patient has a baseline total bilirubin that is within normal limits, delay dosing for nivolumab-related Grade 2 elevations (>1.5-3 x ULN) and start corticosteroids at 0.5 to 1 mg/kg/day prednisone equivalents. Nivolumab may be resumed if the bilirubin improves to Grade 1 (≤ 1.5 x ULN) or better.
 
If a patient has a baseline total bilirubin that is in the Grade 1 range (ULN to ≤ 1.5 x ULN), delay dosing for nivolumab-related Grade 3 elevations (>3-5 x ULN) and start corticosteroids at 1 to 2 mg/kg/day prednisone equivalents.

CTCAE System/Organ/Class (SOC)	Event	Agent	Action
			
Nivolumab may be resumed if the total bilirubin improves to Grade 2 ($\leq 3 \times$ ULN) or better.
 
Doses of nivolumab should be discontinued permanently for the following LFT abnormalities: AST or ALT $>8 \times$ ULN (Grade 3) or drug-induced liver injury (DILI); Total bilirubin $>5 \times$ ULN (Grade 3) or DIL; concurrent AST or ALT $>3 \times$ ULN and total bilirubin $>2 \times$ ULN. Administer corticosteroids 1 to 2 mg/kg/day prednisone equivalents.
 
Subjects with combined Grade 2 AST/ALT meeting discontinuation parameters: go to event monitoring per Section 4.2.

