Gastrointestinal disorders	Pancreatitis	Nivolumab	
Grade 2: Hold nivolumab until resolution, maximum 3 weeks.
 
If >3 weeks, discontinue nivolumab and patient goes to event monitoring.
 
Grade 3 or Grade 4, hold nivolumab until Grade 2 or better then reintroduce
 
If it recurs, the drug is discontinued and patient goes to event monitoring
 
Any \geqGrade 3 drug-related amylase or lipase abnormality that is not associated with symptoms or clinical manifestations of pancreatitis does not require dose delay
 
The PI should be consulted for \geqGrade 3 amylase or lipase abnormalities

Gastrointestinal disorders	Diarrhea	Nivolumab	
Grade ≥ 2 despite maximal supportive care: Hold drug until resolution to baseline grade. If suspicious and clinically indicated, initiate work up to rule out infectious causes and colitis
 
Grade 3 or 4 despite maximal supportive care: Discontinue drug and start corticosteroids until resolution to baseline and patient goes to event monitoring. If suspicious and clinically indicated, initiate work up to rule out infectious causes and colitis

	Colitis	Nivolumab	
Grade ≥ 2: Hold drug until resolution to baseline grade
 
Grade ≥ 3: Discontinue drug and start

CTCAE System/Organ/Class (SOC)	Event	Agent	Action
			corticosteroids until resolution to baseline grade and patient goes to event monitoring
General disorders and administration site conditions	Fatigue	Nivolumab	Grade 3: Hold drug until Grade 2 or better
Metabolism and nutrition disorders	Hyperglycemia	Nivolumab	Grade 4: Permanently discontinue nivolumab
Respiratory, thoracic and mediastinal disorders	Pneumonitis	Nivolumab	Grade ≥ 2 : Hold drug and start corticosteroids until resolution to baseline grade Grade ≥ 3 : Discontinue nivolumab and initiate treatment with high doses of corticosteroids and patient goes to event monitoring
	Cough	Nivolumab	Grade ≥ 2 : Hold drug and start corticosteroids until resolution to baseline grade Grade ≥ 3 : Discontinue nivolumab and initiate treatment with high doses of corticosteroids and patient goes to event monitoring
	Dyspnea	Nivolumab	Grade ≥ 2 : Hold drug until resolution to baseline grade
All other hematologic and non-hematologic	All other hematologic and non-hematologic	Nivolumab	Grade ≥ 2 : Hold nivolumab until resolution to Grade 1 or baseline, except for lymphopenia and leukopenia NOTE: Grade 3 lymphopenia or leukopenia do not require dose delay

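### A patient who stops nivolumab for toxicity without progression is routed both to event monitoring and to observation; if the event-monitoring rule is followed, no scheduled AE visit or CT remains after End of Treatment

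*Combined protocol and SAP*

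**What the plan says.** Three places send a patient who stops for toxicity to event monitoring.

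- Section 13.3: "Patients who go off protocol treatment for reasons other than PD will go to the event-monitoring phase per Section 18.0".
- The schema groups "Unacceptable adverse Events Patient refusal" with progressive disease, and the arrow leads to event monitoring per Section 4.2.
- Section 8.2, for pneumonitis and cough of Grade 3 or above: "Discontinue nivolumab and initiate treatment with high doses of corticosteroids and patient goes to event monitoring". For liver tests: "Subjects with combined Grade 2 AST/ALT meeting discontinuation parameters: go to event monitoring per Section 4.2". The pancreatitis, diarrhea and colitis rows also end in event monitoring. None of these rows mentions an observation step.

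Two places send the same patient to observation.

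- Section 7.2: "After therapy discontinuation, the patient must return to the institution for four visits", at 35±7, 100-120, 230-250 and 330-390 days. The reason for stopping does not matter.
- Section 13.4: "If the patient has achieved CR/CMR, PR/PMR, or SD, the patient will be observed for" the same four visits. The condition is response status, again not the reason for stopping.

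Scheduled CT after treatment belongs to observation. Section 11.1: "During observation, CT scan should be obtained every 3 months during the first year to evaluate for disease progression". Footnote 8 of the study calendar adds that later scans are done as clinically indicated.

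The AE windows do not depend on the phase. Section 10.84 asks for non-serious AEs "for a minimum of 100 days following the last dose of study treatment", and Sections 10.81 and 10.82 ask for all SAEs within 100 days of stopping.

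**The concern.** Sections 13.3 and 13.4 are adjacent, and a patient in CR, PR or SD who stops for toxicity meets both. Sections 13.5 and 13.6 speak of observation only after two years of therapy, so a site could reasonably limit 13.4 to patients who complete treatment and apply 13.3 to the rest. Another site could follow 7.2. Each would have the text on its side.

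The patients who lose scheduled follow-up under 13.3 are selected by toxicity. Safety is the first secondary goal (2.21), and Section 15.191 warns that side effects can appear months after therapy ends. Section 16.322 tabulates each patient's maximum grade per event type, so a late worsening that nobody records would lower that patient's entry.

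PFS (16.323) and duration of response (16.324) are both defined only in responders and run to relapse; PFS also counts death. Relapse is dated when it is found, so less frequent scanning tends to move the date later.

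**Working it through.** **1. The plan's own design figures.** The rule in Section 16.21 stops at 1 or fewer successes in 12 and requires 6 or more in 35. With b(x; 12, p) the binomial probability of x successes in the first 12:

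P(declare promising) = sum over x = 2 to 12 of b(x; 12, p) × P[Bin(23, p) ≥ max(0, 6 − x)]; P(stop early) = P[Bin(12, p) ≤ 1].

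| p | Promising: computed | Promising: Section 16.24 | Early stop: computed | Early stop: Section 16.24 |
|---|---|---|---|---|
| 0.10 | 0.0977 | 0.098 | 0.6590 | 0.659 |
| 0.30 | 0.9014 | 0.901 | 0.0850 | 0.085 |

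The figures reproduce. Nothing in them depends on follow-up after treatment, and Section 16.311 counts response during therapy.

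**2. What each route provides for a patient who stops without PD.**

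| Item | Event monitoring (4.2) | Observation (4.1, 7.2, 11.1) |
|---|---|---|
| Clinic visits | none scheduled | four, to day 330-390 |
| AE assessment | none scheduled | at each visit |
| CT | none scheduled | every 3 months in year 1, then as clinically indicated |
| Progression status | form every 3 months until PD | from visits and CT |
| End of Treatment visit with AE assessment and PET-CT | yes | yes |
| 100-day AE and SAE duty | yes | yes |

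The End of Treatment row applies to both because footnote 1 of the calendar includes withdrawal and removal. The two routes differ in the first three rows. Under 13.3, no scheduled visit supports the 100-day AE duty once End of Treatment has passed. Under 7.2, the visits at 35±7 and 100-120 days would support it.

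**3. Patients affected.** Section 1.26 reports that 14.3% of 105 subjects with haematologic malignancy stopped for drug-related AEs. I assume that this rate carries over.

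- 0.143 × 105 = 15.0, so I take 15/105. The exact (Clopper-Pearson) 95% interval is 8.2% to 22.5%.
- Of 35 evaluable patients: 0.143 × 35 = 5.0, range 2.9 to 7.9.
- Of 39 accrued: 0.143 × 39 = 5.6, range 3.2 to 8.8.
- With a rate anywhere from 5% to 25%: 1.8 to 8.8 of 35.

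**4. Responders among them.** The documents give no response rate for patients who stop for toxicity, so the rate is assumed.

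- At the design's 30%: 5.0 × 0.30 = 1.5.
- At 50%: 5.0 × 0.50 = 2.5.
- All responders at 30%: 35 × 0.30 = 10.5.

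Thus about 1.5 of 10.5 responders would contribute to PFS and duration of response without scheduled CT after End of Treatment.

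**The case against.** The strongest reply is that the text can be harmonised. Section 13.3 says where the patient will go, not when. The word directly is kept for ineligible patients and major violations (13.7, 13.8). Sections 7.2 and 13.4 place observation before event monitoring, so 13.3 may simply name the final phase. The schema survives in the available text only as a fragment, so an observation branch in it cannot be checked. This reading is possible, but neither 13.3 nor the 8.2 rows state it, and 13.5 and 13.6 point the other way. The conflict stands.

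The second reply concerns the consequences, and most of it stands. A reader might infer that late toxicity and progression will be under-recorded in these patients, or that the AE requirements cannot be met alongside 13.3. The documents do not support that. The 100-day duties bind in any phase, and Section 10.41 still requires related SAEs after 30 days. End of Treatment includes AE assessment and PET-CT, and status is reported every 3 months until PD. Section 10.7 leaves late AEs to a Forms Packet, and Section 18.0 refers to a Data Submission Schedule. Neither is in the documents, so what would actually be collected cannot be settled.

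A reader might also put the affected responders at 2 or 3 of about 10. That needs a response rate near 50% in patients who stop for toxicity, for which the documents give no basis. Finally, the 14.3% comes from mixed haematologic diagnoses treated at 1 or 3 mg/kg, so it is only a guide here.

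**Conclusion.** The contradiction is real and should be resolved. Its harm is a risk, not a demonstrated loss of data. If sites follow 13.3, patients who stop for toxicity without PD have no scheduled AE visit or CT after End of Treatment, and progression in the responders among them may be dated later. That would bias duration of response and PFS upward, by an amount the documents do not allow one to estimate. Late safety data would rest on unscheduled reporting.

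The size is about 5 of 35 patients (2.9 to 7.9) if the 14.3% rate, read as 15/105, applies. About 1.5 of them would be responders at an assumed 30% response rate, and 2.5 at 50%. The primary endpoint and the two-stage rule are little affected.

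**What to change.** Reconcile Section 13.3, the schema and the Section 8.2 rows with Sections 7.2, 13.4, 10.82 and 10.84. State that, for data collection, patients who stop without PD follow the existing observation column: the four visits with AE assessment, and CT every 3 months in the first year and then as the calendar states. They would enter event monitoring at PD, on completing observation, or on refusing further follow-up. This concerns only which data are collected after treatment; it does not touch the rules for holding or stopping nivolumab.

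The cost is a wording change plus, for each patient who stops without PD, up to four visits already in the calendar and the year-1 CTs. For five toxicity stops that is up to 5 × 4 = 20 visits. Patients who stop without PD for other reasons would be covered too; the documents give no figure for their number.
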